4.2 Outcome

A prototype intervention to improve the assessment and care of the sexual health needs of men with IBD. The intervention will provide nurses with improved understanding of the support, knowledge, and skills required to effectively assess the sexual health needs of men with IBD and provide appropriate patient-centred care that has the potential to have important immediate benefits to the quality of life of men and their partners, as well as act as a catalyst for further research studies with a clear trajectory to scalable patient benefit.

FUNDED BY

National Institute for
Health and Care Research

York and Scarborough
Teaching Hospitals
NHS Foundation Trust

Est. 1841 YORK ST JOHN UNIVERSITY

MenSH-IBD

5 STUDY DESIGN and METHODS of DATA COLLECTION AND DATA ANALYSIS

This is a mixed-methods study involving three workstreams (WS) aligned with the 3 research objectives, which overall address the core elements of phase 1 of the revised MRC framework for the development and evaluation of complex interventions (Skivington et al., 2021a).

WS1. Cross-Sectional Surveys

Three cross-sectional surveys evaluating current sexual health assessment and provision are to be conducted. The surveys will be open to recruitment for up to 12 months and each should take no longer than 15 minutes to complete.

(WS1.1) Survey of NHS IBD services

A cross-sectional national survey of IBD services in the UK. Data will be collected using an online survey instrument distributed via email to clinical lead/service managers at each NHS Trust. The survey will cover several domains, including the current provision of sexual health care and assessment, availability of specialist nursing services, access to psychological and other support services, and patient education and information provision. The survey will determine whether there are services focused on sexual health and if/how the provision of these differ between male and female patients.

(WS1.2) Survey of IBD nurses

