A national cross-sectional survey of IBD nurses working in the 228 known adult services in the UK. The survey will be distributed to IBD nurses working in each service via the clinical lead/service managers contacted in 1.1 and via the Royal College of Nurses IBD network, CCUK and IBD Specialist Nurse regional meetings and conferences. Advertising the survey will be repeated at different intervals within a 6-month period to improve visibility. There will be a direct follow up with clinical leads when there has been no nurse response. The survey will cover several domains, including the current practice, assessment tools, facilitators, barriers, and confidence in delivering sexual health assessment, care, and advice to male patients with IBD.

(WS1.3) Survey of male IBD patients

A cross-sectional national survey of men with IBD across the UK. The survey will be mainly distributed with the support of CCUK and social media networks. The NHS sites identified in survey 1.1 will be asked to display adverts for the survey but will not act as participant identification sites. The survey will

FUNDED BY

National Institute for
Health and Care Research

York and Scarborough
Teaching Hospitals
NHS Foundation Trust

Est.
1841
YORK
ST JOHN
UNIVERSITY

MenSH-IBD

cover several domains, including the experience of sexual health care assessment and intervention, and perceived needs, preferences, and barriers.

Analysis of quantitative data

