Data will be analysed descriptively using appropriate summary statistics (frequencies/percentages for categorical variables; means/standard deviations or medians/quartile ranges for continuous variables, depending on their distribution). For key variables and scores, 95% confidence intervals will be presented and differences between geographical regions evaluated. Differences between centres that responded and those that did not will be tested using available information. Several associations including barriers and facilitators with the offer of a sexual health assessment for men will be tested using logistic regression. A similar approach will be applied to other key variables and scores as identified by the advisory group and across the three surveys. In each case, estimates of the magnitude of association, for example odds ratio, and corresponding 95% confidence intervals will be presented. Where it is feasible to do so differences between geographical regions and demographic characteristics, such as ethnicity and under-researched populations will be presented. We will assess the mechanism of missing values: if there is a need to impute missing values we will use multiple imputations as a sensitivity analysis.

WS2. Qualitative study

Concurrent with WS1 a qualitative study will be carried out. This will involve: (i) in-depth individual semi-structured interviews with men with IBD and their partners; and (ii) focus groups with nurses and other clinicians involved in the provision of care to men with IBD. The aim of this stream is to explore factors identified in our preliminary PPI work that influence the sexual health assessment and care of men with IBD, and generate ideas on appropriate and acceptable ways in which this could be improved as a basis for the design of the intervention in WS3.

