7.3.2 Consent

WS1: Surveys

FUNDED BY

National Institute for
Health and Care Research

York and Scarborough
Teaching Hospitals
NHS Foundation Trust

Est. 1841 YORK ST JOHN UNIVERSITY

MenSH-IBD

The online survey data is anonymous at point of entry and therefore written informed consent will not be taken. However, the survey will have an opening information page explaining the study and how the data will be used. Participants will be asked to select a box to confirm they have read and understand this information. At the end of the survey there will be two further optional additions (1) to enter a prize draw: participants will be asked to select a box to consent to their contact details to be held separately from the survey responses, only for the purpose of awarding the prize and until completion of the survey, after which all data will be deleted, (2) to express an interest in participating in an interview: participants will be asked to select a box to consent for their contact details alongside the demographic details page to be sent to the study team and stored until the end of the study for the purpose of contact the participant about this study only.

WS2 and WS3: Interviews, focus groups and co-production workshops

Written informed consent will be obtained prior to participation in interviews, focus groups or co-production workshops. The process of obtaining informed consent will be in accordance with Good Clinical Practice (GCP). Participants will be provided with a participant information sheet and given time to consider the information and the opportunity to ask the study team questions. As most of this work will be conducted remotely, on-line consent will be available in this study.

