8 ETHICAL AND REGULATORY CONSIDERATIONS

8.1 Assessment and management of risk

Risk to participants: This is a low-risk study as no clinical intervention is being performed. There is no expected risk to participants, but for those participating in the surveys or interviews there is potential for an emotive response to be elicited. The final page of the public-facing survey will signpost people to relevant organisations that can provide additional support. For the interviews and focus groups, the researcher will be either a registered nurse or experienced qualitative researcher and can respond to any emotional distress and escalate accordingly. Interviews will be terminated if it is felt that they are negatively impacting on a participant. Participants will be offered the Participant Support Leaflet which will provide a list of helpful resources and signpost access to support for depression, anxiety and stress. If any safeguarding issues are disclosed during the interviews they will be escalated via the appropriate channels. There may be some inconvenience to participants regarding the time taken to participate. Participants will be offered a range of possible dates and times.

FUNDED BY

National Institute for
Health and Care Research

York and Scarborough
Teaching Hospitals
NHS Foundation Trust

Est. 1841 YORK ST JOHN UNIVERSITY

MenSH-IBD

Risk to researchers: The study setting carries very little risk to the researchers. Researchers interviewing or facilitating focus groups will be supported by SM or PG who are experienced nurses and researchers. Research debriefs will be offered with either SM or PG.

Informed consent: The process for obtaining informed consent will be in accordance with Good Clinical Practice. In WS1 no identifiable information is collected and therefore there will be no associated consent form. Surveys will instead have an opening page explaining the details of the study and how data collected will be stored and used. The participant will have to select a tick box to say they have understood the information and then completion of the survey will indicate consent. At the end of the surveys, participants may opt-in to a prize draw for participation by providing their email and providing consent for this to be stored until the prizes are allocated. This list will be kept separately to the research data and deleted as soon as the prizes have been randomly allocated.

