8.6 Data protection and patient confidentiality

Data management will comply with the Data Protection Act (2018), GDPR regulations (2016) and York and Scarborough Teaching Hospitals NHS Foundation Trust research SOPs. All investigators and study staff will comply with the Data Protection Act in regards to the collection, storage process and disclosure of personal information.

FUNDED BY

National Institute for
Health and Care Research

York and Scarborough
Teaching Hospitals
NHS Foundation Trust

Est. 1841 YORK ST JOHN UNIVERSITY

MenSH-IBD

All data will be stored and archived by York and Scarborough Teaching Hospitals NHS Foundation Trust in line with their current research SOPs. In WS1 no identifiable information will be collected as part of the research. Participants can opt-in to a prize draw for completion of the survey at which point they will be asked to select a tick-box allowing their email address to be kept until the prizes have been randomly awarded. This list will be kept separately from the study data and deleted once the prizes have been awarded.

In WS2 and WS3 study number and pseudonym will be assigned to each participant. The study number will be allocated by the research team and used on the study documents including the CRF and transcripts. A pseudonym will be used within the interviews and transcriptions and will be selected randomly from a pre-defined list. A separate document will provide a list of study numbers and participant names. As this document will contain identifiable information it will only be accessible by appropriate study members signed on the site delegation log for the purposes of conducting the research and auditing. This will include the CI and York Teaching Hospital Quality Assurance Lead. The document will be stored separately from the site file and trial data and be password protected.

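### Do anonymous WS1 surveys rule out the responding-centre comparison, the nurse follow-up and the 6.5% margin?

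*Protocol*

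**What the plan says.** **Steps that need the service.** Section 5, under the analysis of quantitative data, states: "Differences between centres that responded and those that did not will be tested using available information". For the nurse survey (WS1.2) it adds: "There will be a direct follow up with clinical leads when there has been no nurse response". Nurses are reached through their service leads and also "via the Royal College of Nurses IBD network, CCUK and IBD Specialist Nurse regional meetings and conferences". The service survey (WS1.1) is "distributed via email to clinical lead/service managers at each NHS Trust". Section 7.3 names social media as a route for the surveys, alongside direct email to the listed services.

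**Anonymity.** Section 7.3.2 says: "The online survey data is anonymous at point of entry", and gives this as the reason for taking no written consent. Section 8.1 says: "In WS1 no identifiable information is collected and therefore there will be no associated consent form". Section 8.6 says: "In WS1 no identifiable information will be collected as part of the research". There are two optional exceptions, each with its own tick box: the prize draw, with contact details held apart from the answers, and interest in an interview, where the respondent gives "consent for their contact details alongside the demographic details page to be sent to the study team".

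**Unit and precision.** Section 7.2.1 bases WS1.1 on a 50% response from 228 services (114) and gives a margin of 6.5%. Section 7.2.2 describes WS1.1 as a census of services. Appendix 1 lists the survey instruments, but their content is not shown.

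**The concern.** Taken literally, a fully anonymous return cannot be matched to the list of 228 services. The team could then neither compare responding with non-responding centres nor tell which services had no nurse reply. Invitation route would not settle this for nurses, because some arrive through the professional network, the charity or meetings. An identifier that was never collected cannot be restored at the analysis stage, so an analysis plan would come too late.

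The second strand is precision. Eligibility for WS1.1 is set by person (anyone employed by the NHS with oversight of a service), and social media widens the reach, so two people from one service could both reply. If duplicates went unnoticed, the 114 replies would cover fewer than 114 services, and the true margin would be wider than 6.5%. The comparison of responders matters because the protocol itself expects only half of services to answer.

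**Working it through.** **1. Reproduce the stated margin.** Inputs from section 7.2.1: N = 228 services, n = 114, p = 0.50, 95% confidence. With the finite population correction,

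MoE = 1.96 × √(0.25/n) × √((N − n)/(N − 1)).

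- n = 114, N = 228: 9.18% × √(114/227) = 6.50%. The stated figure is 6.5%.
- Without the correction: 9.18%.
- The same formula with N = 300 nurses gives 8.66% at n = 90 and 11.33% at n = 60. The stated figures are 8.7% and 11.3%.

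The correction is therefore the protocol's method throughout. For WS1.1 it holds when the 114 replies are distinct services, which is how section 7.2.1 frames them.

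**2. How far duplicates could move it.** The protocol gives no duplicate rate, so these counts are assumptions.

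| Distinct services among 114 replies | MoE |
|---|---|
| 114 | 6.50% |
| 100 | 7.36% |
| 90 | 8.05% |

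The shift is 7.36 − 6.50 = 0.86 points, or 8.05 − 6.50 = 1.55 points. Response at the audit rates quoted in section 7.2.1 would move the margin further the other way: 66% (about 150 services) gives 4.69%, and 72% (about 164) gives 4.06%.

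**3. Set the statements side by side.**

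- Section 7.3.2 uses anonymity to explain why no written consent is taken, section 8.1 does so under informed consent, and section 8.6 deals with data protection and confidentiality. All three concern the identity of persons.
- A service is an organisation. Section 7.3.1 says the services were identified from publicly available audit data, and section 7.3 says the team holds the list of 228.
- Section 5 also plans comparisons between geographical regions, so some location information is already meant to be recorded.
- A WS1.1 form can therefore carry a service name or code while no personal detail is taken. On that reading the statements do not contradict each other.

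**4. Nurse follow-up.** Even if all 90 target replies came from different services, 228 − 90 = 138 services (61%) would have no nurse reply. That number follows from the target of 90 and would be the same with perfect tracking, so it does not measure any defect. The follow-up is a recruitment reminder to clinical leads. If response status is known imperfectly, some leads receive a reminder they did not need, and no estimate is altered by that.

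**The case for a change.** The strongest case for a change is that the protocol nowhere describes a service field, an individual link, a tracking log or a rule for two replies from one service, and that these are matters of data collection rather than analysis. Reading the phrase about available information as a safeguard does not help much, since it more naturally describes the characteristics to be compared than the means of knowing who replied. A service name can also point to a person: a WS1.1 respondent is a lead or manager of that service, and on the protocol's figures there are about 300/228 = 1.3 nurses per service. Because the absence of a consent form rests on anonymity, that bears on the consent rationale as well.

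What stands is that the text leaves unsaid how the service is recorded, how nurse response by service is tracked, and how the no-consent-form rationale reads where a service has one lead or very few nurses. What does not stand is the step from unsaid to impossible. Nothing shows that the service goes uncollected, and the forms that would settle it are not available. Requiring a service field within the nurse answers would reduce the anonymity that the consent arrangement relies on. An optional entry kept apart from the answers would be incomplete whenever nurses skipped it.

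**Conclusion.** The concern does not call for a change. It is a gap that the team would fill sensibly. Having planned a comparison of responding centres, with the service as the unit and the list of 228 in hand, they would have to capture the service in WS1.1. Keeping one reply per service is ordinary data preparation that a protocol can leave to the analysis plan.

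The 6.5% is correct for 114 distinct services. With assumed duplication down to 100 or 90 services it would be 7.4% or 8.1%, and no decision threshold depends on it.

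This rests on two assumptions: that anonymity refers to persons, as the setting of all three statements suggests, and that the unseen WS1.1 form or its link records the service. If the second were false, the comparison of centres could not be carried out as planned. The margin would still be right as a planning figure.

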7.2 Sampling

7.2.1 Size of sample

WS1. Cross-Sectional Surveys

(WS1.1) For the survey of NHS IBD services, the **target sample size is 114**. Population estimates have been based on the information provided in the IBD-UK 2019/20 audit report which had a response rate of 72% (IBD-UK, 2021). In a personal communication, IBD-UK confirmed that the response rate for the most recent audit (not yet published) is 66%. Given the current NHS pressures, sample size calculations have been based on a lower response rate of 50% of the 228 services. Given the current NHS staffing challenges, we anticipate the response rate to our survey will be lower and have based our sample size calculations on a response rate of 50% (which we think is a conservative estimate). A response rate of 50% would allow estimation of key binary indicators (assuming a 50% proportion, which is the worst-case scenario) with a margin of error (MoE) of 6.5% for a 95% confidence level (CL).

(WS1.2) For the IBD nurses survey the **target sample size is 90**. The findings from the Caseload Report Standards for IBD Specialist Nurses in the UK (Crohn's & Colitis UK, 2017) and the survey by Leary and colleagues (Leary et al., 2018) estimated that there are 300 IBD nurses in the UK. The estimate was based on national data curated from the IBD audit and the Crohn's and Colitis UK. The response rate for that survey by Leary et al. (2018) was 55% (168 responses received). As the survey was conducted in 2017 and given the impact of the COVID-19 pandemic and ensuing challenges in the IBD workforce as highlighted in the survey by Kennedy et al (2020) of IBD services across the UK, we have assumed that the response rate might be lower and have assumed it to be 30%. A response rate of 30% (n=90) would allow estimation of key binary indicators (assuming a 50% proportion) with a margin of error (MoE) of 8.7% for a 95% confidence interval (CI). If instead the response rate is 20% (n=60) then the MoE increases to 11.3%.

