7.2.2 Sampling technique

WS1. Cross-Sectional Surveys

(WS1.1) Census approach of all IBD services as identified by the 2019 IBD-UK audit.

(WS1.2) Census approach of all IBD specialist nurses.

(WS1.3) Targeted convenience sampling of men with IBD via established networks.

WS2 and WS3 Qualitative study and co-production workshops

Purposive sampling will be adopted in workstreams 2 and 3. For the interviews a heterogenous sample who indicate a willingness to be interviewed in the patient survey in WS1 will be purposively recruited based on a range of characteristics including age, ethnicity, marital/partner status, sexuality, and IBD type (UC or Crohn's). Participants with partners will be asked to invite them to participate should they wish. For the focus groups a multidisciplinary sample of participants (e.g., nurses, doctors, allied health professionals, psychologists) involved in the provision of IBD care in the NHS setting will be purposively recruited.

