7.3.1 Sample identification

All the IBD services have been identified via the IBD-UK audit, the data of which is publicly available. Identification of IBD nurses will be via the IBD services. Men with IBD will be identified through Crohn's and Colitis UK, poster and leaflet advertising in IBD services and targeted advertising in health and social care organisations that serve under-represented regions and demographic groups. There will be no payment for participation in the survey. However, a prize draw will be offered both for IBD nurses and patient participants offering 1x £50 high-street voucher for the IBD nurse survey and 5 x £50 high-street vouchers for men with IBD. To enter the prize draw a separate part of the survey will collect contact details, which will be stored separately from the survey data and deleted as soon as the prizes winners have been randomly selected and contacted.

Identification of participants for interviews and focus groups will be through the survey and/or study advertisements where participants will be provided the opportunity to express an interest and provide their contact details. Men with IBD and partners of men with IBD will be offered a £20 high-street voucher for participation in the interviews. Professionals will be offered a £20 high-street voucher for participation in the focus groups. All participants will be compensated for travel and other reasonable expenses such as childcare.

Participants for the co-production workshop will be identified by the study team and stakeholder advisory group. Those who participated in interviews and focus groups may also be purposively identified and invited to participate.

Throughout this study, no NHS patient records or data will be used for the identification of participants. NHS sites will be asked to advertise the study using posters, leaflets and social media but no patient details will be passed from NHS sites to the study team.

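### Service non-response in WS1.1 is handled only by a significance test, which neither measures nor corrects a departure from the random response that the 6.5% margin assumes

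*Protocol*

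**What the plan says.** Protocol section 5, under the analysis of quantitative data, deals with non-responding services in one sentence: "Differences between centres that responded and those that did not will be tested using available information". It does not name the characteristics to be compared, a measure of the size of any difference, or a use of the result in the estimates. The same paragraph allows multiple imputation as a sensitivity analysis if missing values need imputing, but does not link this to services that never reply.

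Section 7.2.2 describes the sampling for WS1.1 as a "Census approach of all IBD services as identified by the 2019 IBD-UK audit". Section 7.2.1 states that "sample size calculations have been based on a lower response rate of 50% of the 228 services", which gives 114 responders, and a 6.5% margin of error at 95% confidence ("assuming a 50% proportion, which is the worst-case scenario"). It describes the 50% as a figure "which we think is a conservative estimate"; the two audits it cites had response rates of 72% and 66%. On the frame, section 7.3.1 says: "All the IBD services have been identified via the IBD-UK audit, the data of which is publicly available". Section 7.3 adds that the study team has been given the list of the 228 services.

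**The concern.** In a census with partial response, the main threat to a national proportion is that services which answer differ from those which do not. Services with some sexual health provision may be more willing to fill in a survey about it. For any characteristic known for every service on the list, the difference between responders and the full list is observed directly. What matters is how large it is and how strongly it relates to provision. A significance test answers another question, namely whether the difference could be chance.

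The test is also the only stated check, specific to non-responding services, on the assumption behind the 6.5% margin. If it is significant, the protocol states nothing that changes the estimate. If it is not, the reader still does not know how large the differences were. At stake is the accuracy of the figures on current NHS provision, which answer the first research question and feed the intervention design in WS3.

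**Working it through.** **Inputs.** From protocol section 7.2.1: N = 228 services, n = 114 responders, p = 0.5, 95% confidence, stated margin 6.5%. Assumed for illustration only: large and small services equally common; response 65% and 35%; provision 40% and 20%. Also assumed: a two-sided 5% test, since no level is stated.

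**1. The plan's own margin.**
- Without finite population correction: 1.96 × √(0.25/114) = 9.18 points.
- With it: 1.96 × √[(0.25/114) × (228 − 114)/(228 − 1)] = 6.50 points.

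The stated 6.5% therefore uses the correction, which is valid if the 114 are a random subset of the 228.

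**2. How non-response moves the estimate.** With response rate r,

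responders' proportion − all-services proportion = (1 − r) × (responders' proportion − non-responders' proportion).

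Each point of difference *in the survey outcome* moves the estimate by 0.50 points at 50% response, 0.34 at 66% and 0.28 at 72%. The non-responders' outcome is never seen, so no test of available information can measure this difference directly.

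**3. Assumed example.** Overall response is (65% + 35%)/2 = 50%, as planned. Responders are 65% large and non-responders 35% large.
- True proportion: 0.5 × 0.40 + 0.5 × 0.20 = 30%.
- Unweighted responders: 0.65 × 0.40 + 0.35 × 0.20 = 33%.
- Responders re-weighted to half large, half small: 0.5 × 0.40 + 0.5 × 0.20 = 30%.

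The error is 3 points, a little under half of the 6.5-point margin. Weighting removes all of it here because, by construction, response depends on size alone.

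**4. What the planned test does in that example.** It compares 65% with 35% large, 114 against 114. By the arcsine method, h = 2 × (arcsin√0.65 − arcsin√0.35) = 0.609; h × √(114/2) = 4.60; power = Φ(4.60 − 1.96) = 99.6%. The test finds the imbalance, and the estimate remains 33%.

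**5. Price of weighting.** The weights are 0.50/0.65 for large and 0.50/0.35 for small services. The usual approximation for variance inflation, which takes the weights as unrelated to the outcome, gives 0.65 × (0.50/0.65)² + 0.35 × (0.50/0.35)² = 1.10. The interval is about √1.10 = 1.05 times as wide.

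**The case against.** **The statistical analysis plan may add weighting.** It is not shown, and choice of weights and follow-up steps often belongs there. This stands, so absent weighting alone is no finding. What remains is that the protocol does choose a tool for non-response, and a significance test is a poor one for a listed frame.

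**The 50% is a planning floor.** This also stands. With the audits' response rates, a given outcome difference does less harm (step 2).

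**The audit data are incomplete.** If the 72% refers to the same 228 services, about 0.28 × 228 = 64 returned no audit data, and they may be non-responders here too. The protocol lists no audit variables. This limits how much weighting can achieve. Even so, any variable known for all services and usable in the planned comparison can also be used for weighting.

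**Is the test too weak?** A reader might infer that it would miss an imbalance worth the whole margin about half the time. A 13-point difference in the outcome moves the estimate by 0.5 × 13 = 6.5 points, and a test of a 13-point difference (near 50%, 114 against 114) has 50% power. The documents do not support that inference. The first 13 points concern the unobserved outcome; the second concern a characteristic of the service. They coincide only if the characteristic fully determines the outcome. With the example's 20-point provision difference, a 13-point imbalance in service size moves the estimate by 0.5 × 0.13 × 0.20 = 1.3 points. Moving it by 6.5 points would take a 65-point imbalance, which the test could hardly miss. Low power is not the problem.

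**Conclusion.** The point holds, at modest size. The margin rests on random response, and the only stated safeguard specific to non-responding services neither measures the size of a departure nor corrects for it, even when the departure is obvious. The 3-point error is illustrative. It depends on assumed response and provision rates by service size, and the documents give no figures for either. It would be smaller with better response or a weaker link between service type and provision, and larger in the opposite case.

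A reader might also infer that the sponsor will report unadjusted figures whatever the test shows, or will take a non-significant result as proof of representativeness. The protocol says neither; it is silent on what follows from the test. No decision threshold in the study turns on a few points in WS1.1, so this calls for a better analysis sentence and does not undermine the design.

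**What to change.** Replace the sentence in section 5 with:
- (a) a table of responding services against all 228, on nation or region and any audit variables available, giving the size of each difference;
- (b) WS1.1 key proportions weighted to the 228 services on those variables, shown beside the unweighted figures as a sensitivity analysis whatever any test shows.

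Add a note in section 7.2.1 that the 6.5% margin assumes non-response is unrelated to provision.

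The cost is a little analysis on a list already held and data described as public. Intervals may widen slightly (about 5% in the example). Services without audit data can be weighted on nation or region only, assuming the list shows location. Bias not tied to the weighting variables remains and should be stated as a limitation.
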